3.2 Exclusion Criteria

Subjects meeting any of the criteria below may not participate in the study:

1. Patients with pure seminoma.
2. Patients with pure teratoma.
3. Chemotherapy within 2 weeks of initiating study treatment. There is no maximum allowable number of previous therapies.
4. Major surgery within 3 weeks of starting study treatment. There is no minimum time requirement for minor procedures such as biopsy or vascular access placement.
5. Radiation within 2 weeks of starting study treatment.
6. \geq Grade 3 neuropathy at the time of enrollment.
7. Pregnancy or breast-feeding.
8. Previous treatment with any anti-CD30 directed therapy.

4. SUBJECT REGISTRATION

All patients will be registered with the Indiana University Cancer Center Clinical Trials Office. Regulatory files will be maintained by the Clinical Trials Office. Applicable regulatory documents must be completed and on file prior to registration of any patients. Potential patients will be identified in the Oncology outpatient clinics or by referrals from outside physicians. Patients who appear to be eligible for this trial will undergo the Informed Consent Process and be screened for eligibility utilizing the Eligibility Criteria. The original signed IRB approved Informed Consent Document and completed eligibility checklist will be forwarded to the Clinical Trials Office designee for eligibility verification and registration in the OnCore[®] database. Notification will be sent to the principal investigator, treating physician and research nurse when registration is complete to confirm registration and inform them of patient ID number.

Study data will be collected and stored in OnCore[®], developed by Forte Research Systems, Inc. (www.forteresearch.com). OnCore[®] Enterprise Research is a comprehensive, web-based, Clinical Trial Management System (CTMS) which utilizes an Oracle database. It has been licensed by Indiana University (IU) to support the operations and data capture of clinical research trials.

The system has been installed and configured within a HIPAA-aligned, Information Technology (IT), operations center supported by IU's IT organization, University Information Technology Services (UITS). OnCore[®] provides users secure access with unique IDs/passwords and restricts access by assigned roles, from any location, to record, manage, and report on data associated with the operation and conduct of clinical trials.

The system is comprised of three specific applications—Clinical Research Management (CRM), Biospecimen Management (BSM), and Unified Registries Management (URM). Indiana University leverages OnCore[®] to support clinical research operations specifically as it relates to the following functions/processes: electronic Scientific Review Committee (SRC), regulatory management, protocol and subject life cycle management, coverage analysis, study financials management, subject registration and visit management, subject safety monitoring, protocol deviation monitoring, study auditing and monitoring, electronic data management, correlative study sample management, specimen banking and management, registries management, effort tracking, and reporting.

Subjects must be registered prior to starting protocol therapy. Subjects must begin therapy within **7 business days** of registration.

5. TREATMENT PLAN

- Eligible patients will be divided into two cohorts, those who are CD30 positive and those who are CD30 negative/unknown. Both groups will be treated similarly and in parallel but analyzed separately.
- CD30 status may be unknown in the unlikely case of tumor-marker-only relapse or when a fresh tumor biopsy is not feasible, and archival tumor tissue is not obtainable

despite efforts to do so. These patients will be included in the CD30 negative cohort for analysis purposes, since statistically NSGCT are more likely to be CD30 negative.

The number of such patients with unknown CD30 status should not exceed 5 patients.

- Enrollment to the study does not have to wait for determination of CD30 status prior to treatment, unless in the situation where one arm is closed for enrollment or an interim assessment of response for the Simon stage I phase is needed. For example:
 - The first 10 patients can enroll on the study and start on therapy without waiting for CD30 status assessment. Prior to enrolling patient number 11, CD30 status need to be determined for all patients to make sure an interim assessment of response for the Simon stage I phase is not needed (i.e. one arm is at 10 patients).
 - If an arm has closed for lack of efficacy, CD30 status need to be assessed prior to starting therapy to make sure that patients belong to the open arm.
 - If both arms advance to the second stage of the Simon design then enrollment can again be pursued without waiting for CD30 status until one arm is closed to accrual.
- Eligible patients will be treated with brentuximab vedotin at 1.8 mg/kg IV every 3 weeks (maximum dose of 180 mg) indefinitely until disease progression, unacceptable toxicity, or study closure.
- Eligible patients with grade 2 peripheral neuropathy at enrollment will be treated with brentuximab vedotin at 1.2 mg/kg IV every 3 weeks (maximum dose of 180 mg) indefinitely until disease progression, unacceptable toxicity, or study closure.
- Response to treatment will be assessed clinically with history, physical exam and tumor markers measurement (BHCG and AFP) on day 1 of each cycle and with CT scans after cycle 2, 4, and every 4 cycles thereafter while receiving treatment.

5.1 Treatments Administered

Brentuximab vedotin (SGN-35), the investigational agent under study in this protocol, is an ADC consisting of the antibody cAC10, specific for human CD30; the potent antimicrotubule agent MMAE; and a protease-cleavable linker that covalently attaches MMAE to cAC10.

5.2 Investigational Study Drug

For injection: 50 mg of brentuximab vedotin as a sterile, white to off-white lyophilized, preservative-free cake or powder in a single-use vial for reconstitution.

5.2.1 Dose and Administration

Brentuximab vedotin, 1.8 mg/kg (1.2 mg/kg in patients with grade 2 peripheral neuropathy at enrollment) will be administered by IV infusion given over approximately 30 minutes on Day 1 of each 21-day cycle. In the absence of infusion-related reactions, the infusion rate for all patients should be calculated in order to achieve a 30-minute infusion period. If an infusion reaction does occur, infusion rates should be adjusted as necessary and documented appropriately in source documents. Brentuximab vedotin must

not be administered as an IV push or bolus. Brentuximab vedotin should not be mixed with other medications.

Dosing is based on patient weight according to the institutional standard; however, doses will be adjusted for patients who experience a $\geq 10\%$ change in weight from baseline. Actual weight will be used except for patients weighing greater than 100 kg; dose will be calculated based on 100 kg for these individuals. Rounding is permissible within 5% of the nominal dose.

5.2.2 Required Premedication and Postmedication

Routine premedication should not be administered for the prevention of infusion-related reactions prior to the first dose of brentuximab vedotin. However, patients who experience a Grade 1 or Grade 2 infusion-related reaction may receive subsequent brentuximab vedotin infusions with premedication as described in Section 5.2.3. Patients who experience a Grade 3 or Grade 4 infusion-related reaction may potentially receive additional treatment with brentuximab vedotin at the discretion of the Investigator after discussion with the Sponsor.

Patients should be individually evaluated to assess the need for tumor lysis prophylaxis prior to the first dose of brentuximab vedotin. Patients should receive prophylaxis as appropriate per institutional standards.

5.2.3 Management of Infusion Reactions

Infusion-related reactions may occur during the infusion of study treatment. The infusion should be administered at a site properly equipped and staffed to manage anaphylaxis should it occur. The patient should be observed for at least 60 minutes following the first infusion of study treatment. During this observation period, an IV line should remain open for at least 60 minutes to allow administration of IV drugs, if necessary for infusion-related reactions. All supportive measures consistent with optimal patient care will be given throughout the study according to institutional standards. This includes adjusting the infusion time if necessary. Medications for infusion-related reactions, such as epinephrine, antihistamines, and corticosteroids, should be available for immediate use.

Patients who experience a Grade 1 or Grade 2 infusion-related reaction may receive subsequent study treatment infusions with premedication consisting of acetaminophen and diphenhydramine administered 30–60 minutes prior to each 30-minute infusion or according to institutional standards.

If anaphylaxis occurs, brentuximab vedotin administration should be immediately and permanently discontinued.

5.2.4 Management of Suspected PML

Signs and symptoms of progressive multifocal leukoencephalopathy (PML) may include altered mental status, motor deficits such as hemiparesis or ataxia, visual disturbances, or higher cortical dysfunction such as dysphasia or agnosia. See the Investigator's Brochure for further details.

If PML is suspected, hold further brentuximab vedotin dosing and undertake a diagnostic work-up including (but not limited to):

- Neurologic examinations, as warranted
- Brain radiologic features by magnetic resonance imaging (MRI)
- PCR analysis: John Cunningham virus (JCV) DNA detectable in cerebrospinal fluid

If PML is confirmed, permanently discontinue treatment with brentuximab vedotin.

5.3 Concomitant Therapy

All concomitant medications and blood products will be collected from Day 1 (predose) through the safety reporting period. Any concomitant medication given for a study protocol-related adverse event should be recorded from the time of informed consent. All supportive measures consistent with optimal patient care should be provided throughout the study according to institutional standards.

5.3.1 Required Concomitant Therapy

Pneumocystis carinii (jiroveci) pneumonia (PCP) prophylaxis is required for human immunodeficiency virus (HIV)-positive patients. Medications that aggravate cytopenias (e.g., trimethoprim-sulfamethoxazole) should be avoided.

All patients should be up-to-date on any recommended vaccinations prior to study entry. Additional vaccination(s) during each cycle of study treatment must be approved by the medical monitor.

5.3.2 Allowed Concomitant Therapy

Routine premedication should not be administered prior to the first dose of brentuximab vedotin. However, patients who experience an infusion-related reaction may receive subsequent treatment with premedication as described in Section 5.2.3.

Prophylactic intrathecal therapy is allowed only after discussion with the Sponsor.

For HIV-positive patients, highly active anti-retroviral therapy (HAART) according to the institutional standard of care is permitted.

The use of platelet and/or red blood cell supportive growth factors or transfusions when applicable is allowed. The use of colony stimulating factors for the treatment of neutropenia per institutional practice is permitted during therapy. Prednisone (or equivalent) ≤ 20 mg/day may be used if for reasons other than malignant disease control and the patient has been on a stable dose for ≥ 30 days; doses > 20 mg are allowed for treatment of hypersensitivity reactions.

5.3.3 Prohibited Concomitant Therapy

Patients may not receive other investigational drugs, immunosuppressive medications (excluding steroids as described in Section 5.3.2), radiotherapy, or systemic anti-neoplastic therapy during the study.

5.4 Drug Interactions

In vitro data indicate that monomethyl auristatin E (MMAE) is a substrate and an inhibitor of CYP3A4/5. *In vitro* data indicate that MMAE is also a substrate of the efflux transporter P-glycoprotein (P-gp).

5.4.1 Effect of Other Drugs on Brentuximab vedotin

CYP3A4 Inhibitors/Inducers: MMAE is primarily metabolized by CYP3A [see *Clinical Pharmacology (10.2)*]. Co-administration of brentuximab vedotin with ketoconazole, a potent CYP3A4 inhibitor, increased exposure to MMAE by approximately 34%. Patients who are receiving strong CYP3A4 inhibitors concomitantly with brentuximab vedotin should be closely monitored for adverse reactions. Co-administration of brentuximab vedotin with rifampin, a potent CYP3A4 inducer, reduced exposure to MMAE by approximately 46%.

P-gp Inhibitors: Co-administration of brentuximab vedotin with P-gp inhibitors may increase exposure to MMAE. Patients who are receiving P-gp inhibitors concomitantly with brentuximab vedotin should be closely monitored for adverse reactions.

5.4.2 Effect of Brentuximab Vedotin on Other Drugs

Co-administration of brentuximab vedotin did not affect exposure to midazolam, a CYP3A4 substrate. MMAE does not inhibit other CYP enzymes at relevant clinical concentrations [see *Clinical Pharmacology (10.2)*]. Brentuximab vedotin is not expected to alter the exposure to drugs that are metabolized by CYP3A4 enzymes.

5.5 Treatment Compliance

Study drug administration will be performed by study site staff and documented in source documents and the CRF.

6. TOXICITIES AND DOSE DELAYS/DOSE MODIFICATIONS

The NCI Common Terminology Criteria for Adverse Events (CTCAE) v4 will be used to grade adverse events.

Subjects enrolled in this study will be evaluated clinically and with standard laboratory tests before and at regular intervals during their participation in this study as specified in Study Calendar & Evaluations.

Subjects will be evaluated for adverse events (all grades), serious adverse events, and adverse events requiring study drug interruption or discontinuation as specified in Study Calendar & Evaluations.

6.1 Dose Delays and Dose Modifications

Inpatient dose reduction will be allowed depending on the type and severity of toxicity. [Table 1](#) describes the recommended dose modifications for study treatment-associated

toxicity.

The start of the next cycle may be delayed for up to 3 weeks if additional time is required for the patient to recover from study treatment-associated toxicity experienced during the current cycle. Delays of greater than 4 weeks are prohibited without approval of the Sponsor.

Doses reduced for treatment-related toxicity should not be re-escalated without discussion with the Sponsor.

Table 1 Recommended dose modifications for brentuximab vedotin-associated toxicity

Toxicity	Grade 1	Grade 2	Grade 3	Grade 4
Peripheral Neuropathy	Continue at same dose level.	Reduce treatment to 1.2 mg/kg	Withhold until toxicity resolves to \leq Grade 2 or has returned to baseline; resume treatment at 1.2 mg/kg	Discontinue treatment
Nonhematologic	Continue at same dose level.	Continue at same dose level, except in the event of Grade 2 neuropathy.	Withhold dose until toxicity is \leq Grade 2 or has returned to baseline, then resume treatment at the same dose level. ^a	Withhold dose until toxicity is \leq Grade 2 or has returned to baseline, then reduce dose to 1.2 mg/kg and resume treatment, or discontinue at the discretion of the Investigator
Hematologic	Continue at same dose level.	Continue at same dose level.	Withhold dose until toxicity is \leq Grade 2, or has returned to baseline, then resume treatment at the same dose level. ^b Consider growth factor support (G-CSF or GM-CSF) for treatment of neutropenia and prophylaxis in subsequent cycles. If Grade 4 neutropenia recurs despite growth factor support, consider discontinuation or dose	

Toxicity	Grade 1	Grade 2	Grade 3	Grade 4
			reduction to 1.2 mg/kg.	

a. Patients who develop Grade 3 or 4 electrolyte laboratory abnormalities may continue study treatment without interruption.

b. Patients who develop Grade 3 or 4 lymphopenia may continue study treatment without interruption.

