6.2 Protocol Therapy Discontinuation

In addition to discontinuation from therapy related to toxicities as outlined in Section 6.1, a subject will also be discontinued from protocol therapy and followed up per protocol under the following circumstances:

- Evidence of disease progression
- The treating physician thinks a change of therapy would be in the best interest of the subject
- The subject requests to discontinue protocol therapy, whether due to unacceptable toxicity or for other reasons
- In case a subject decides to prematurely discontinue protocol therapy (“refuses treatment”), the subject should be asked if she or he may still be contacted for further scheduled study assessments. The outcome of that discussion should be documented in both the medical records and in the eCRF.
- A female subject becomes pregnant
- Delays of greater than 4 weeks are prohibited without approval of the Sponsor.

Subjects will be removed from protocol therapy and the site investigator notified when any of the criteria listed above apply. The reason for discontinuation of protocol therapy will be documented on the electronic case report form (eCRF).

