10.8 Adverse Events

The following serious adverse reactions are discussed in greater detail in other sections of the prescribing information:

- Peripheral Neuropathy [see *Warnings and Precautions (10.9.1)*]
- Anaphylaxis and Infusion Reactions [see *Warnings and Precautions (10.9.2)*]
- Hematologic Toxicities [see *Warnings and Precautions (10.9.3)*]
- Serious Infections and Opportunistic Infections [see *Warnings and Precautions (10.9.4)*]
- Tumor Lysis Syndrome [see *Warnings and Precautions (10.9.5)*]
- Increased Toxicity in the Presence of Severe Renal Impairment [see *Warnings and Precautions (10.9.6)*]
- Increased Toxicity in the Presence of Moderate or Severe Hepatic Impairment [see *Warnings and Precautions (10.9.7)*]
- Hepatotoxicity [see *Warnings and Precautions (10.9.8)*]
- Progressive Multifocal Leukoencephalopathy [see *Warnings and Precautions (10.9.9)*]
- Pulmonary Toxicity [see *Warnings and Precautions (10.9.10)*]
- Serious Dermatologic Reactions [see *Warnings and Precautions (10.9.11)*]
- Embryo-Fetal Toxicity [see *Warnings and Precautions (10.9.12)*]

Please refer to the most current IB or package insert(s) for the comprehensive list of adverse events.

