10.9.2 Anaphylaxis and Infusion Reactions

Infusion-related reactions, including anaphylaxis, have occurred with ADCETRIS. Monitor patients during infusion. If anaphylaxis occurs, immediately and permanently discontinue administration of ADCETRIS and administer appropriate medical therapy. If an infusion-related reaction occurs, the infusion should be interrupted and appropriate medical management instituted. Patients who have experienced a prior infusion-related

reaction should be premedicated for subsequent infusions. Premedication may include acetaminophen, an antihistamine, and a corticosteroid.

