10.9.11 Serious Dermatologic Reactions

Stevens-Johnson syndrome (SJS) and toxic epidermal necrolysis (TEN), including fatal outcomes, have been reported with ADCETRIS. If SJS or TEN occurs, discontinue ADCETRIS and administer appropriate medical therapy.

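### Table 1 sends a Grade 3 SJS/TEN event back to the same dose after recovery, although Section 10.9.11 requires discontinuation and 6.1–6.2 do not mention it

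*Combined protocol and SAP*

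**What the plan says.** Section 6 sets the grading scale: "The NCI Common Terminology Criteria for Adverse Events (CTCAE) v4 will be used to grade adverse events". Table 1 in Section 6.1 then gives the action by grade.

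- **Nonhematologic, Grade 3:** withhold until the toxicity is at most "Grade 2 or has returned to baseline, then resume treatment at the same dose level". The cell has no option to stop. Its one footnote lets patients with electrolyte abnormalities continue without interruption.
- **Nonhematologic, Grade 4:** withhold until the same recovery, "then reduce dose to 1.2 mg/kg and resume treatment, or discontinue at the discretion of the Investigator".

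Section 6.2 opens its list of reasons for ending therapy with "In addition to discontinuation from therapy related to toxicities as outlined in Section 6.1". The list that follows names no specific toxicity.

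The SJS/TEN rule is in the drug-information section, at 10.9.11: "If SJS or TEN occurs, discontinue ADCETRIS and administer appropriate medical therapy". The list in 10.8 that leads to it is introduced in label language: "The following serious adverse reactions are discussed in greater detail in other sections of the prescribing information".

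The other two events have rules in the treatment plan. Section 5.2.3 says: "If anaphylaxis occurs, brentuximab vedotin administration should be immediately and permanently discontinued". Section 5.2.4 requires a hold for suspected PML and a permanent stop once it is confirmed. Sections 10.9.2 and 10.9.9 repeat these rules, the former as "If anaphylaxis occurs, immediately and permanently discontinue administration of ADCETRIS and administer appropriate medical therapy".

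**The concern.** Table 1 is where this protocol puts toxicity stops and exceptions. Neuropathy has its own row, with a mandatory stop at Grade 4, and footnotes carve out electrolyte abnormalities and lymphopenia. Section 6.2 relies on 6.1 for toxicity stops. A site that works from these two sections and has a patient with treatment-related SJS/TEN at Grade 3 is told to wait for recovery and resume at the same dose. At Grade 4 it is told that stopping is optional. Section 10.9.11 makes stopping a requirement and does not condition it on grade.

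The stake is the safety of individual patients: 10.9.11 itself reports fatal outcomes from these reactions. The trial is multicenter, so the table has to be safe for staff who use it without the drug-information section beside it.

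**Working it through.** No arithmetic beyond counting applies. The plan states no figure on this point, so the check sets the rules side by side.

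| Event | Stop rule in the treatment plan | Stop rule in drug information | Named in Table 1 or 6.2 |
|---|---|---|---|
| Anaphylaxis | 5.2.3, permanent | 10.9.2, permanent | No |
| Confirmed PML | 5.2.4, permanent | 10.9.9 | No |
| SJS/TEN | None | 10.9.11 | No |

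**Counts.** Stop statements: 2 (anaphylaxis) + 2 (PML) + 1 (SJS/TEN) = 5. Events named in Table 1 or 6.2: 0 of 3. References from 6.1–6.2 to 5.2 or 10.9: 0. Of the 12 subsections of 10.9, 2 point to 6.1 (10.9.1 on neuropathy and 10.9.3 on hematologic toxicity), and neither covers one of the three events. Events with no stop rule outside Section 10: 1 of 3, SJS/TEN. Its other appearances are the 10.8 list entry for serious dermatologic reactions and an example of causality evidence in 11.1.2. Neither tells a site what to do.

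**Can a site obey both rules for SJS/TEN?**

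1. *Grade 3.* Table 1 ends in resumption at the same dose and offers no other outcome, while 10.9.11 ends in discontinuation. Read literally, the two cannot both be followed.
2. *Grade 4.* Table 1 allows either resumption at 1.2 mg/kg or discontinuation. A site that chooses to stop satisfies both rules. The cell does not contradict 10.9.11, but it makes a required stop discretionary.

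**Does *discontinue* in 10.9.11 mean a lasting stop?** It lacks the word *permanently*. However, 10.9.9 separates holding (suspected PML) from discontinuing (confirmed PML), and 5.2.4 describes that same PML stop as permanent. The natural reading is therefore a lasting stop, but the text leaves some room.

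**Anaphylaxis and PML.** Their rules are in Section 5.2, with the dosing and administration instructions. They are specific and do not depend on grade, and Table 1 is headed as recommended modifications. The specific rule governs, so only a pointer is missing from 6.1–6.2.

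**The case against.** The strongest reply is that every stop rule already exists and binds. Section 13.2 requires the study to be run as the approved protocol describes, so 10.9.11 counts wherever it stands. Sections 10.8 and 10.9 were adapted to this protocol, with cross-references renumbered to its own sections. Table 1 is only recommended, 6.2 adds to other stops without claiming to list them all, and only neuropathy and hematologic toxicity are sent from 10.9 to 6.1. Safeguards also overlap: resumption requires recovery, treatment ends for unacceptable toxicity (Section 5), the physician may change therapy in the patient's interest (6.2), delays over 4 weeks need Sponsor approval, and serious events are reported within 1 business day (11.2.1.1).

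Most of this stands, and it makes wrongful re-dosing unlikely. It does not remove the discrepancy in the Grade 3 cell. The protocol gives no explicit order of precedence, the general safeguards rest on judgment where 10.9.11 does not, and for SJS/TEN no treatment-plan rule catches the reader first.

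Three stronger readings are tempting, and the documents do not support them.

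- *A stop rule is missing, or all three events conflict equally with Table 1.* None is missing, and for anaphylaxis and PML the treatment plan settles the matter.
- *Table 1 contradicts the Sponsor discussion that 5.2.2 requires before re-treatment after Grade 3–4 infusion reactions.* Table 1 is silent on that step. Section 5.2.2 adds a condition, and both can be followed.
- *Section 5.2.2 permits re-treatment after anaphylaxis, because 10.9.2 counts anaphylaxis among infusion-related reactions.* The 5.2.2 sentence is only permissive. The next subsection, 5.2.3, and the same paragraph of 10.9.2 both order a permanent stop.

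**Conclusion.** The point holds for SJS/TEN. The Grade 3 cell gives an action opposite to 10.9.11, the Grade 4 cell turns a required stop into a choice, and neither 6.1 nor 6.2 leads the reader to the rule. For anaphylaxis and confirmed PML the defect is a missing cross-reference only.

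The size is minor: one event type with a real discrepancy and two with a missing pointer. Nothing changes in the endpoints, the sample size, the Simon design's error rates or the analysis. No probability of harm can be given, because the documents state neither how often these events occur nor what CTCAE grades they take.

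The conclusion assumes that an SJS/TEN event can be graded 3 or 4, that it is judged associated with study treatment (the scope of Table 1), and that *discontinue* in 10.9.11 means a lasting stop.

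**What to change.** 1. Add a footnote to the nonhematologic Grade 3 and Grade 4 cells of Table 1: SJS/TEN (10.9.11), anaphylaxis (5.2.3) and confirmed PML (5.2.4) of any grade require discontinuation regardless of this row; other Grade 3–4 infusion reactions follow 5.2.2.
2. Add a bullet to 6.2 that names the same three events with the same references.
3. Have the sponsor confirm whether discontinuation for SJS/TEN is permanent, and say so in the footnote.
4. Optionally, add the words *except anaphylaxis* to the sentence in 5.2.2 on re-treatment after Grade 3–4 infusion reactions. This is a clarification only.

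The cost is a few lines in a clarifying amendment, with no added procedures, visits or patients.
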